3.2.2 Lung function

The absolute and the changes from baseline to each of the post-baseline visits as scheduled in Table 1 (adults) and Tables 2A and 2B (adolescents) of the CSP on pre-BD FEV₁ and post-BD FEV₁ will both be summarised.

3.3 Patient reported outcome variables

All the PROs are collected on paper CRFs. In the calculation of the scores of ACQ-6 and AQLQ(s)+12, if any one of the component values within the questionnaire is missing, then the mean score of ACQ-6, and total score and all 4 domain scores of AQLQ(s)+12 will be considered as missing.

3.3.1 Asthma Control Questionnaire

In the ACQ-6 questionnaire the patients are asked to recall the status of their asthma during the previous week with regards to symptom and bronchodilator use. The questionnaire includes questions on

- Awakened at night by symptoms
- Limitation of normal daily activities
- Waking in the morning with symptoms
- Dyspnoea
- Wheeze
- Daily rescue medication

The questions of the ACQ-6 are measured on a 7-point scale scored from 0 (totally controlled) to 6 (severely uncontrolled). The ACQ-6 score is computed as the un-weighted mean of the responses.

Asthma control responder status (Improved, No change, Deterioration) at EOT (56 weeks for adults and 108 weeks for adolescents) will be categorised according to the following limits ([Juniper et al 2005](#)):

- $ACQ-6 \text{ (End of treatment–baseline)} \leq -0.5 \rightarrow \text{Improvement}$
- $-0.5 < ACQ-6 \text{ (End of treatment–baseline)} < 0.5 \rightarrow \text{No change}$
- $ACQ-6 \text{ (End of treatment–baseline)} \geq 0.5 \rightarrow \text{Deterioration}$

In the event of missing EOT ACQ-6 score during deriving responder status at EOT visit, a hybrid last observation carried forward (LOCF) approach will be used such that patients who did not discontinue treatment but have a missing EOT result will have their last observation carried forward while subjects who discontinued treatment will be considered as non-responders. The hybrid LOCF will not be applied to adolescents' data for adult completion analysis given that adolescent patients' EOT visit is Week 108, and adolescents do not have a scheduled AQLQ(S)+12 assessment in BORA at the Week 56 time point (coinciding with the adult EOT visit).

Similarly, asthma control responder status will also be categorised in the same way for other post-baseline visits but the hybrid LOCF will not be applied for any missing non-EOT values.

Asthma control status will be categorised according to their ACQ-6 end-of-treatment score as follows (Juniper et al 2006):

- ACQ-6 (End of treatment) ≤ 0.75 → Well controlled
- $0.75 < \text{ACQ-6 (End of treatment)} < 1.5$ → Partly controlled
- ACQ-6 (End of treatment) ≥ 1.5 → Not well controlled

Similarly, asthma control status for other post-baseline visits will also be categorised the same way. The hybrid LOCF will be used for any missing EOT values as described above.

3.3.2 Standardised Asthma Quality of Life Questionnaire for 12 years and older

The AQLQ(s)+12 is a 32 question health-related quality of life assessment. Respondents are asked to recall their experiences during the previous 2 weeks and to score each of the 32 questions on a 7-point scale ranging from 7 (no impairment) to 1 (severe impairment). The overall score is calculated as the mean response to all questions. The 4 individual domain scores (4 domains assessing 1) symptoms, 2) activity limitations, 3) emotional function, and 4) environmental stimuli) are the means of the responses to the questions in each of the domains.

Health-related quality of life (HRQoL) responder will be categorised at EOT (56 weeks for adults and 108 weeks for adolescents) according to the following definitions based on the overall score:

- AQLQ(S)+12 (End of treatment–baseline) ≥ 0.5 → Improvement
- $-0.5 < \text{AQLQ(S)+12 (End of treatment–baseline)} < 0.5$ → No change
- AQLQ(S)+12 (End of treatment–baseline) ≤ -0.5 → Deterioration

In the event of missing EOT AQLQ(S)+12 overall score, the hybrid (LOCF) approach described above will be used for categorisation of responders. The hybrid LOCF will not be applied to adolescents' data for adult completion analysis given that adolescent patients' EOT visit is Week 108, and adolescents do not have a scheduled AQLQ(S)+12 assessment in BORA at the Week 56 time point (coinciding with the adult EOT visit).

Similarly, HRQoL responder status will also be categorised in the same way for other post-baseline visits but the hybrid LOCF will not be applied for any missing non-EOT values.

3.3.3 Work Productivity and Activity Impairment (WPAI+CIQ)

The 10 questions included in the WPAI+CIQ are as follows:

- 1 = currently employed (yes/no)
- 2 = hours missed work due to health problems
- 3 = hours missed work due to other reasons
- 4 = hours actually worked
- 5 = degree health affected productivity while working (0-10 scale, with 0 meaning no effect)
- 6 = attends class in an academic setting (yes/no)
- 7 = hours missed class due to health problems
- 8 = hours actually attended class
- 9 = degree health affected productivity while attending class (0-10 scale, with 0 meaning no effect)
- 10 = degree health affected regular activities (other than work or class) (0-10 scale, with 0 meaning no effect)

If the answer to question 1 is 'No, not currently employed', then the patient should skip to question 6. If the answer to question 6 is 'No, not currently attending class', then the patient should skip to question 10.

The WPAI+CIQ provides 4 types of scores: absenteeism (work or class time missed), presenteeism (impairment at work or class/reduced on-the-job effectiveness), work productivity loss (overall work or class impairment/absenteeism plus presenteeism), and activity impairment. WPAI+CIQ outcomes are expressed as impairment percentages, with higher numbers indicating greater impairment and less productivity.

For the work related questions, the following calculations should be used to create the variables of interest:

- Number of work hours missed = Q2
- Absenteeism = $Q2/(Q2+Q4)$
- Presenteeism = $Q5/10$
- Work Productivity Loss = $Q2/(Q2+Q4)+[(1-Q2/(Q2+Q4))x(Q5/10)]$
- Activity Impairment = $Q10/10$

For the class-related questions, the following calculations should be used to create the variables of interest:

- Number of class hours missed = Q7
- Absenteeism = $Q7/(Q7+Q8)$
- Presenteeism = $Q9/10$

- Class Productivity Loss = $Q7/(Q7+Q8)+[(1-Q7/(Q7+Q8))x(Q9/10)]$
- Activity Impairment = $Q10/10$.

3.3.4 EQ-5D-5L

The EQ-5D-5L questionnaire assesses 5 dimensions: mobility, self-care, usual activities, pain/discomfort and anxiety/depression. Each dimension has 5 response options (no problems, slight problems, moderate problems, severe problems, and extreme problems) that reflect increasing levels of difficulty. The value of response is 1 corresponding to ‘no problems’, and 5 corresponding to ‘extreme problems’.

The patient will be asked to indicate his/her current health state by selecting the most appropriate level in each of the 5 dimensions. The questionnaire also includes a visual analogue scale, where the patient will be asked to rate current health status on a scale of 0-100, with 0 being the worst imaginable health state.

3.4 Health care resource utilisation due to asthma

Health care resource utilisation due to asthma will be collected by the Investigator/authorised delegate at each visit as specified in the protocol and recorded in the Asthma-related health care event module in the eCRF.

Following are the resource categories utilised for each patient:

- Ambulance transport
- Hospitalisation, intensive care (days in intensive care)
- Hospitalisation, general care (days in general care)
- Emergency room visit
- Visit to specialist
- Visit to primary health care physician
- Other health care visit
- Home visit, physician
- Home visit, other health care
- Telephone call to physician
- Telephone call to nurse

- Spirometry
- Advanced pulmonary function test

The annual rates of health care utilisation by type of health care encounter will be calculated for hospitalisation (combining intensive care and general care), emergency department visits, unscheduled outpatient visits (ie, visit to specialist and/or visit to primary health care physician and/or other health care visit), home visit (combining physician or other health care), telephone calls (to physician or nurse), ambulance transport, clinical tests (spirometry and advanced pulmonary function test), and all of these healthcare encounters combined. The annual rates of health care encounters will be calculated in a manner similar to the calculation of the annual exacerbation rates defined in Section 3.2.1.1 (ie, annual rate for the treatment group) for on-treatment, post-treatment and on-study periods.

3.5 Pharmacokinetic variables

Due to the limited sampling schedule, the PK assessment will be primarily based on the observed steady-state serum trough (pre-dose) concentrations, C_{trough} .

3.6 Immunogenicity variables

ADA assessments will be conducted utilising a tiered approach (screen, confirm, titre). The presence of neutralising antibodies (nAb) will be tested in all ADA-positive samples using a ligand binding assay.

For each patient, the following response variables will be evaluated based on ADA status in predecessor studies and data from the start of the BORA through to the BORA FU visit (Week 68 for adults and Week 120 for adolescents). For adolescents in adult completion analysis phase, the responses variables will be evaluated from the start of the BORA through the Week 56 visit or IPD visit, whichever is earlier.

- ADA positive at any visit (including baseline, post-baseline, unscheduled visits)
- ADA positive at both baseline and at least one post-baseline
- ADA positive at baseline only
- ADA positive at post-baseline only
- ADA newly persistently positive: defined as ADA negative at BORA baseline and at least 2 post-baseline ADA positive measurements with at least 16 weeks (112 days) between the first and last positive measurement, or an ADA positive result at the last available assessment.
- ADA stable persistently positive: defined as ADA positive at BORA baseline and at least 2 post-baseline ADA positive measurements with at least 16 weeks (112 days) between the first and last positive measurement.

- ADA transiently positive: defined as having at least one post-baseline ADA positive measurement and not fulfilling the conditions for either newly or stable persistently positive.
- nAb positive
- Newly treatment-induced ADA positive: defined for patients who in predecessor study were not ADA positive any time, but post-baseline in the current study is ADA positive for the first time.
- Decrease in titre: defined as having at least two post-baseline ADA positive results, and a >75% decrease from the maximum post-baseline titre which must be maintained from the time when it first occurred until the last on-treatment period visit. The >75% decrease can include going from a positive to negative titre result (e.g. a change of titer from ≥ 200 to negative).
- Treatment boosted ADA: at least one of patient's post baseline titres is > 4-fold of the baseline titre.

Treatment-emergent ADA positive (BORA-specific incidence) is defined as either newly treatment-induced ADA positive or treatment boosted ADA as defined above.

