3.6 Discontinuation from investigational product

Patients will be discontinued from IP in the following situations:

1. Patient decision. The patient is at any time free to discontinue treatment without prejudice to further treatment (see Section 3.7)
2. Adverse event (AE) that in the opinion of the Investigator contraindicates further dosing
3. Risk to patient as judged by the Investigator or AstraZeneca
4. Severe non-compliance to study protocol
5. Eligibility requirement found not to be fulfilled (see Section 3.4)
6. Pregnancy
7. Lost to follow-up³
8. Development of any study specific criteria for discontinuation:
 - (a) Anaphylactic reaction to the IP requiring administration of epinephrine
 - (b) Development of helminth parasitic infestation requiring hospitalization
 - (c) If 2 consecutive doses of IP missed or more than 2 scheduled doses of IP are missed during course of the study

³ Patient is considered lost to follow up when any of the following attempts of contact are failed: -3 attempts of either phone calls, faxes, or emails; - having sent 1 registered letter/certified mail; 1 unsuccessful effort to check the vital status of the patient using publicly available sources, if allowed by local regulations.

(d) An asthma-related event requiring mechanical ventilation

All patients who prematurely discontinue IP should return to the study center and complete the procedures described for the Premature Investigational Product Discontinuation Visit (IPD) within 4 weeks \pm 7 days after the last dose of IP and for the final Follow-up visit at 16 weeks (\pm 7 days) after the last dose of IP (see [Table 1](#) and [Table 2](#)).

Reasons for premature discontinuation of IP should be recorded in the eCRF.

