| Week 0 | 1 | Study Day \leq 1 |
| Week 12 | 85 | 2 \leq Study Days \leq 238 |
| Week 56 (EOT for adults) | 393 | 239 \leq Study Days \leq 574 |
| Week 108* (EOT for adolescents) | 757 | 575 \leq Study Days |

For chemistry labs: Calcium, Chloride, CO₂, Glucose, Phosphorus, Potassium, Sodium, Total cholesterol and Uric acid.

* Visits for adolescents only.

Table 7 Adjusted visit windows for PK (unscheduled samples only) and ADA (including nAb)

| Analysis Visit | Scheduled study day | Adjusted visit window |
|---------------------------------|----------------------------|----------------------------------|
| Week 0 | 1 | Study Day \leq 1 |
| Week 8 | 57 | 2 \leq Study Days \leq 84 |
| Week 16 | 113 | 85 \leq Study Days \leq 154 |
| Week 28 | 197 | 155 \leq Study Days \leq 252 |
| Week 44 | 309 | 253 \leq Study Days \leq 336 |
| Week 52 | 365 | 337 \leq Study Days \leq 385 |
| Week 56# (EOT for adults) | 393 | 386 \leq Study Days \leq 434 |
| Week 68# (FU for adults) | 477 | 435 \leq Study Days |
| Week 60* | 421 | 386 \leq Study Days \leq 476 |
| Week 76* | 533 | 477 \leq Study Days \leq 588 |
| Week 92* | 645 | 589 \leq Study Days \leq 700 |
| Week 108* (EOT for adolescents) | 757 | 701 \leq Study Days \leq 798 |
| Week 120* (FU for adolescents) | 841 | 799 \leq Study Days |

Visit for adult only.

* Visits for adolescents only.

Note that the Week 52 window has a shorter window range (3 weeks) post scheduled study day due to adjustment for adult group having a scheduled EOT visit 4 weeks later.

Table 8 Adjusted visit windows for Pre-BD spirometry

| Analysis Visit | Scheduled study day | Adjusted visit window |
|---------------------------------|---------------------|----------------------------------|
| Week 0 | 1 | Study Day \leq 1 |
| Week 16 | 113 | 2 \leq Study Days \leq 168 |
| Week 32 | 225 | 169 \leq Study Days \leq 280 |
| Week 48 | 337 | 281 \leq Study Days \leq 385 |
| Week 56# (EOT for adults) | 393 | 386 \leq Study Days |
| Week 64* | 449 | 386 \leq Study Days \leq 504 |
| Week 80* | 561 | 505 \leq Study Days \leq 616 |
| Week 96* | 673 | 617 \leq Study Days \leq 728 |
| Week 108* (EOT for adolescents) | 757 | 729 \leq Study Days |

Visit for adult only.

* Visits for adolescents only.

Note that Week 48 window has shorter window range (7 weeks) post scheduled study day due to adjustment for adult group having a scheduled EOT visit 8 weeks later.

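### A baseline-positive patient who is never ADA negative can be labelled transiently positive when follow-up is short, while a baseline-negative patient with the same later results is called persistent

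*SAP*

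**What the plan says.** SAP section 3.6 sorts patients with a post-baseline positive ADA result into three classes.

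- **Newly persistent.** The definition begins "ADA newly persistently positive: defined as ADA negative at BORA baseline". It is met by two post-baseline positives with at least 112 days between the first and last positive, "or an ADA positive result at the last available assessment".
- **Stable persistent.** "ADA stable persistently positive: defined as ADA positive at BORA baseline and at least 2 post-baseline ADA positive measurements with at least 16 weeks" between the first and last positive. There is no last-assessment alternative.
- **Transient.** The remainder: at least one post-baseline positive while "not fulfilling the conditions for either newly or stable persistently positive".

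Evaluation uses "data from the start of the BORA through to the BORA FU visit (Week 68 for adults and Week 120 for adolescents"). For adolescents in the adult completion analysis it stops at Week 56 or the IPD visit, whichever comes first.

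SAP section 4.2.10 uses the stable class as a subgroup for demographics, exacerbation rate, pre-bronchodilator FEV1, AEs and SAEs, hypersensitivity events, eosinophils and serum concentration. The amendment history records that the ADA categories were revised but gives no reason for treating the two baseline groups differently. SAP section 6 gives none either.

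**The concern.** Two patients with identical post-baseline results can get opposite labels. The one called transient is the one with more evidence of persistence, because that patient was also positive at baseline. Such a patient cannot enter the newly persistent class, which requires a negative baseline, and so is in no persistence subgroup at all.

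The stable subgroup is meant to show whether lasting ADA goes with more exacerbations, poorer lung function or hypersensitivity. Protocol section 1.4 names reduced efficacy and hypersensitivity as theoretical risks of ADA. The rule tends to remove patients with short follow-up, and follow-up may be short for reasons linked to those outcomes: protocol section 3.6 lists an anaphylactic reaction requiring epinephrine among the reasons for stopping IP. Whether any such patient exists cannot be told from the documents.

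**Working it through.** The SAP gives no figure for this point, so the check applies the definitions to possible sequences of results. Counts below are patterns, not patients.

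**Inputs**
- Adult post-baseline ADA visits, from the SAP Appendix A table titled "Adjusted visit windows for PK (unscheduled samples only) and ADA (including nAb"): Weeks 8, 16, 28, 44, 52, 56 and 68.
- Threshold: 16 weeks × 7 = 112 days.
- Early stopping, protocol section 3.6: patients "complete the procedures described for the Premature Investigational Product Discontinuation Visit (IPD) within 4 weeks" (±7 days) of the last dose, and return for follow-up at 16 weeks (±7 days) after it.
- Assumption: ADA is sampled at IPD and follow-up. The assessment schedules do not read clearly enough in the text available to confirm this.
- Reading: the 112 days run between post-baseline positives. The alternative is tested at the end.

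**Full adult schedule, baseline positive.** Seven visits give 2^7 = 128 patterns, of which 127 contain a positive and 64 end positive.
- Positive throughout: Week 8 to Week 68 is 60 × 7 = 420 days, so stable.
- Of the 64 ending positive, 62 are stable and 2 transient: Week 68 only, and Weeks 56 and 68 only (12 × 7 = 84 days).
- Transient overall: 14 of 127. For baseline-negative patients it is 12 of 127; the difference is those same 2 patterns.

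**Short follow-up, every sample positive**

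| Post-baseline samples | Span (days) | Baseline positive | Baseline negative |
|---|---|---|---|
| Week 8 | one positive | transient | newly persistent |
| Weeks 8, 16 | 8 × 7 = 56 | transient | newly persistent |
| Weeks 8, 16, 20 | 12 × 7 = 84 | transient | newly persistent |
| Last dose Week 0: IPD Week 4, follow-up Week 16 | 12 × 7 = 84 | transient | newly persistent |
| Last dose Week 4: IPD Week 8, follow-up Week 20 | 12 × 7 = 84 | transient | newly persistent |
| Last dose Week 8: Week 8, IPD Week 12, follow-up Week 24 | 16 × 7 = 112 | stable | newly persistent |

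The last row just meets the threshold. With the ±7-day follow-up window it can fall to 112 − 7 = 105 days, which is transient.

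**Adolescents in the adult completion analysis.** Follow-up samples are outside the evaluation period. With a last dose at Week 16, the IPD visit is at Week 20, so the span from Week 8 is 84 days (91 with the +7-day window): transient though never negative. For those reaching Week 56, the visits are Weeks 8, 16, 28, 44 and 52. Of 2^4 = 16 patterns ending positive, 2 are transient: Week 52 only, and Weeks 44 and 52 only (56 days).

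**If the baseline positive counts as the first.** Weeks 0, 8 and 16 span 112 days, so stable. With the full adult schedule only 1 of 64 end-positive patterns (Week 68 only) stays transient. A never-negative patient is then transient only with a single post-baseline sample or with less than 112 days from baseline to the last positive.

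**Effect of two possible changes, baseline-positive patients**

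| | As written | All available results positive counts as stable | Last-assessment clause added |
|---|---|---|---|
| Samples at Weeks 8, 16, 20: always positive | transient | stable | stable |
| Same samples: end-positive patterns called transient | 4 of 4 | 3 of 4 | 0 of 4 |
| Full schedule: end-positive patterns called transient | 2 of 64 | 2 of 64 | 0 of 64 |
| Full schedule: all patterns called transient | 14 of 127 | 14 of 127 | 12 of 127 |

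**The case against.** The strongest reply is that the SAP does not say first post-baseline positive. For a baseline-positive patient, baseline could be the first, and most of the cases above then become stable. This stands as an ambiguity. The sentence speaks of post-baseline measurements immediately before it sets the interval, so the post-baseline reading is the more natural one, and two programmers could reasonably differ.

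A second reply is that follow-up samples rescue many early leavers. That is correct for adults who attend. With a last dose at Week 16, follow-up at Week 32 makes the span 24 × 7 = 168 days. It does not help those who miss the visit, those whose last dose is at Week 0 or 4, or adolescents in the adult completion analysis.

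Third, the asymmetry may be deliberate: a baseline-negative patient who converts at the last visit has had no chance to show duration, and the ADA analyses are said to follow a global plan that is not available here. That may explain why the clause was written for new positives. It does not explain calling a never-negative patient transient.

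Fourth, the harm is limited. Affected patients stay in the overall ADA-positive group and are counted as positive at baseline and post-baseline. Transient is not itself an outcome subgroup in SAP section 4.2.10. All of this stands.

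A reader might infer that every baseline-positive patient who is never negative or who ends positive is mislabelled, or that all who leave by about Week 24 are. The documents do not support either: full follow-up makes the always-positive patient stable, and Week 8 to Week 24 meets the threshold exactly. Nor do they show that the patients affected are those most harmed by ADA.

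**Conclusion.** The inconsistency is real but narrow. On the post-baseline reading, a baseline-positive patient with one post-baseline positive, or with post-baseline positives spanning less than 112 days, is called transient even if never negative. The same post-baseline results ending positive make a baseline-negative patient persistent. Among never-negative patients this needs short follow-up or missing samples.

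The number of patients cannot be computed, because no ADA prevalence or discontinuation pattern is given. Patients moving to MELTEMI at Week 16 would meet the same rule, but they are summarised separately and the SAP lists no ADA table for them, so they are not counted here.

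The conclusion rests on the post-baseline reading of the interval and, for early leavers, on ADA sampling at IPD and follow-up. What changes is the ADA category table and the stable-persistent subgroup summaries. The analyses are descriptive, so no test, error rate or sample size is affected. A correction before database lock is worthwhile because it is cheap.

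**What to change.** Amend the stable persistently positive definition in SAP section 3.6 in two ways.

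1. Include a baseline-positive patient whose available post-baseline results are all positive, whatever the span.
2. State whether the baseline positive counts as the first positive in the 112-day interval.

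The first change lets in a patient with a single positive post-baseline sample. If that is thought too little evidence, the SAP can set a minimum number of samples or report such patients as not classifiable.

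Alternatively, add the last-assessment clause already used for newly persistent patients. This makes the two definitions match, but a patient positive at baseline, negative from Week 8 to Week 56 and positive once at Week 68 would then be called stable. If this route is taken, that downside should be accepted in writing.

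With either change, reword the newly persistent definition so that its last-assessment alternative clearly applies only to baseline-negative patients. Read loosely, it would also admit baseline-positive patients, and 62 of the 64 end-positive patterns would then be both newly and stable persistent.

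The cost is a sentence or two in the SAP and a small change to the derivation program. No new data are needed.
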